9.1.1. Interim Analysis

Once all enrolled patients in the Synovitis Imaging Population have completed the Week 6 visit the mean standardized change from baseline at 6 weeks in synovial volume (the primary endpoint) and other efficacy measures, will be analyzed. Safety analyses may be included and will be detailed in the SAP. Full results of this interim analysis will be presented to the Sponsor.

9.1.2. Final Analyses

Once all enrolled patients have completed the Week 24 visit, all final analyses specified in the SAP will be completed following database lock and reported in the CSR. Post-hoc, exploratory analyses, may also be performed to further understand and elucidate study results; these analyses will be clearly identified as such in the CSR.

9.2. General Considerations and Methods

Data collected in this study will be presented using summary tables, figures, and data listings. Continuous variables will be summarized using descriptive statistics, including the mean, median, standard deviation, minimum and maximum. Categorical variables will be summarized by frequencies and percentages. CIs may also be provided. Figures will be used to support the presentation of certain data. Sensitivity analyses may be performed to examine the effect of missing data, as well as the effect of any baseline imbalance.

All CIs, statistical tests, and resulting p values will be reported as 2-sided. Significance will be assessed at $\alpha = 0.05$ level and the significance level will not be adjusted for the secondary endpoint analyses.

9.2.1. Analysis Populations

Complete details of the statistical analysis will be specified in the SAP. Four analysis populations are planned for this study as follows:

- The Safety Population will include all patients who receive study drug. The Safety Population will be used to assess safety and tolerability.
- The Synovitis Imaging Population will include all patients from the Safety Population, who have a pre-treatment synovial volume measurement of greater than 3000 mm³ of gadolinium enhancement as determined by quantitative image analysis, as well as quality pre-treatment and Week 6 MRIs. In addition, the patients included in this population will have no major protocol deviations and/or imaging variations

(i.e. change in coil, machine or software) deemed to potentially impact the imaging analysis.

- The Imaging Population will include all patients from the Safety Population, who have quality MRI data available for pre-treatment and at least one post baseline timepoint and with no major protocol deviations and/or imaging variations (i.e., change in coil, machine or software) deemed to potentially impact the imaging analysis.
- The Efficacy Population will include all patients from the Safety Population, who have at least one post-Baseline WOMAC or KOOS assessment.

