- The Synovitis Imaging Population will include all patients from the Safety Population who have a pre-treatment synovial volume measurement of greater than 3000 mm³ of gadolinium enhancement as determined by quantitative image analysis, as well as quality pre-treatment and Week 6 MRIs. In addition, the patients included in this population will have no major protocol deviations and/or imaging variations (i.e. change in coil, machine, or software) deemed to potentially impact the imaging analysis.
- The Imaging Population will include all patients from the Safety Population, who have quality MRI data available for pre-treatment and at least one post- baseline timepoint and with no major protocol deviations and/or imaging variations (i.e. change in coil, machine or software) deemed to potentially impact the imaging analysis.
- The Efficacy Population will include all patients from the Safety Population, who have at least one post-Baseline/Day 1 WOMAC or KOOS assessment.

Demographic and baseline characteristics will be listed by study site and patient and will be summarized. Frequencies and proportions will be presented for the categorical variables and descriptive statistics will be presented for continuous variables.

Primary efficacy analysis will be the mean standardized change from baseline at 6 weeks in synovial volume will be determined and the 95% confidence interval (CI) will be calculated. Secondary efficacy analyses include an absolute change (mm³) from baseline at 6 weeks in synovial volume will also be calculated and the 95% CI will be presented. Standardized and absolute change from baseline will also be analyzed for synovial volume at 24 weeks.

Descriptive statistics and the 95% CIs will be calculated on pain, stiffness, function and quality of life. Other efficacy variables such as structural and contrast changes in bone, cartilage and other tissues based on the MRI results will be provided in the SAP and described in the Imaging Manual. A responder/non-responder analysis will be conducted to describe associations between physiological and functional/QOL measures and MRI results

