7. INVESTIGATIONAL PLAN

7.1. Overall Study Design and Plan

This is an open-label study assessing the effect of the administration of a single IA injection of FX006 32 mg on synovial volume in patients with OA of the knee. The study will be conducted in male and female patients who are ≥ 40 years of age.

Eligible patients who provide written consent and meet all entry criteria will undergo initial ultrasound examination and MRI with contrast of the index knee. For each MRI, a pre-treatment synovial volume measurement will be derived by quantitative image analysis. Patients will then receive a single IA injection of FX006 administered to the index knee at Baseline/Day 1. Patients will return to the clinic at Weeks 6 and 24 for an MRI with contrast of the index knee and other assessments. Patients must also have a blood sample drawn for eGFR testing within 30 days prior to the scheduled MRIs. In addition, a patient questionnaire will be administered, and AEs and concomitant medication updates will be collected via telephone at Weeks 12 and 18.

Refer to Table 1, Schedule of Study Assessments for full details.

The study is expected to enroll over approximately 15 months.

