7.9.6. Index Knee MRI with Contrast

A diagnostic quality MRI with a gadolinium-based contrast agent of the index knee is required within 10 days prior to Day 1/Baseline, and then again at Week 6 and Week 24 (+/- 7 days).

Once eligibility is confirmed, a pre-treatment MRI will be obtained and submitted to the central imaging facility to confirm image quality. Documentation of a quality MRI is needed prior to Day 1/Baseline. If the initial pre-treatment MRI fails quality control (QC), another MRI will need to be completed prior to Day 1/Baseline but at least 3-4 days after the initial MRI to ensure that that contrast agent has washed out.

All subsequent images (Week 6 and 24) will need to be completed on the same machine with the same coil and software as the Pre-treatment image and will need to be submitted to the central imaging vendor to confirm image quality. If the image does not pass QC, another MRI will need

to be completed within the +/- 7 day visit window but at least 3-4 days after the initial MRI to ensure that that contrast agent has washed out.

An MRI image acquisition manual will be distributed to sites with detailed technical instructions and specifications for imaging sequences, imaging coil and Field of View (FOV) positions.

The MRI will be analyzed centrally for the primary endpoint as well as the secondary and exploratory endpoints based on imaging.

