9.4.3. Efficacy Analyses

Primary efficacy endpoint:

- Mean standardized change from baseline at 6 weeks in synovial volume

Secondary efficacy endpoints:

- Mean absolute change (mm³) from baseline at 6 weeks in synovial volume
- Mean standardized change from baseline at 24 weeks in synovial volume
- Mean absolute change (mm³) from baseline at 24 weeks in synovial volume

Analysis of additional secondary and exploratory endpoints will be defined in the SAP.

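### The 3000 mm³ cut is applied to the same single MRI that serves as baseline, so in this uncontrolled trial the Week 6 change in mm³ (or in common-SD units) is shifted modestly toward a reduction

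*Protocol*

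**What the plan says.** The volume cut belongs to the analysis set and is not an entry criterion. Section 9.2.1 admits to the Synovitis Imaging Population those treated patients "who have a pre-treatment synovial volume measurement of greater than 3000 mm³ of gadolinium enhancement as determined by quantitative image analysis", provided that the pre-treatment and Week 6 scans are of adequate quality and no deviation or scanner change affects the analysis.

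The volume comes from the scan taken before dosing: "For each MRI, a pre-treatment synovial volume measurement will be derived by quantitative image analysis" (7.1). Table 1 has one MRI before treatment, and 7.9.6 describes it: "Once eligibility is confirmed, a pre-treatment MRI will be obtained and submitted to the central imaging facility to confirm image quality". A second scan is taken only to replace one that fails quality control, so no patient has two usable pre-treatment readings.

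Section 9.4.3 gives the primary endpoint as "Mean standardized change from baseline at 6 weeks in synovial volume" and a secondary endpoint as "Mean absolute change (mm³) from baseline at 6 weeks in synovial volume". The Synopsis attaches a 95% CI to each: for the primary, "synovial volume will be determined and the 95% confidence interval (CI) will be calculated", and for the secondary, "absolute change (mm³) from baseline at 6 weeks in synovial volume will also be calculated and the 95% CI will be presented". The protocol does not say how the standardization is done.

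The Week 6 analysis is tied to the selected set: "Once all enrolled patients in the Synovitis Imaging Population have completed the Week 6 visit the mean standardized change from baseline at 6 weeks" (9.1.1). The primary objective (6.1) and the sample size (9.3: about 100 enrolled for at least 70 evaluable) point to the same set. Section 7.3.5 confirms a single arm. The Imaging Population in 9.2.1 has no volume cut, but the protocol does not assign it the Week 6 synovial-volume change.

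**The concern.** A patient whose volume happened to read high on the pre-treatment scan is more likely to pass the cut, and one whose volume happened to read low is more likely to fail it. At Week 6 those chance deviations do not repeat, so the selected group drifts down on average even if the injection does nothing. A control arm selected in the same way would show the same drift and cancel it; this trial has none. Repeating the scan on the same machine, coil and software (7.9.6) limits measurement error but not real fluctuation in synovitis over six weeks.

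At stake is how a modest Week 6 reduction is read. The shift runs in the direction the trial hopes to see, and the stated Week 6 analysis contains no estimate free of it.

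**Working it through.** **Inputs from the protocol.** Cut 3000 mm³ (9.2.1); one pre-treatment scan (Table 1, 7.9.6); n = 70 (9.3); two-sided 95% CI (9.2); no control (7.3.5). The 70 cannot be reproduced as a power calculation, because no effect size, SD or power is stated.

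**Inputs assumed.** No drug effect; lognormal volumes with median 4000, 5000 or 6000 mm³ and CV 0.6 or 0.8; scan-to-scan correlation ρ on the log scale from 0.95 to 0.7. The share above the cut is not stated. If 0, 10, 15 or 20% of 100 patients are lost for other reasons, 70 evaluable implies 70/100 = 70%, 70/90 = 78%, 70/85 = 82% or 70/80 = 88% above it. A median of 5000 gives 77 to 82%, so it is taken as the main case.

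**Direction.** Let Y0 and Y1 be the two readings, exchangeable under no effect, and c the cut. Then

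E[(Y1 − Y0)·1{Y0 > c}] = ½·E[(Y1 − Y0)·(1{Y0 > c} − 1{Y1 > c})] ≤ 0.

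The two brackets never have the same sign, so this holds for any distribution. It is strictly negative whenever repeat readings can cross 3000 mm³. Division by a common SD leaves the sign unchanged.

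**Size.** With s = √ln(1 + CV²), a = (ln 3000 − ln median)/s, share above f = 1 − Φ(a) and mean m = median·exp(s²/2):

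- E[Y0 | selected] = m·Φ(s − a)/f
- E[Y1 | selected] = m·Φ(ρs − a)/f

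Example with median 5000, CV 0.6, ρ = 0.8: s = 0.555, a = −0.921, f = 0.822, m = 5831. The two means are 6601 and 6486 mm³, so the shift is −115 mm³ (1.7%).

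The next table is for median 5000. The half-width is t(0.975; 69)·SD of change/√70 = 0.238·SD, with the SD taken from simulation. The last column comes from 40,000 simulated null trials per row; nominal is 2.5%.

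| CV | ρ | Shift, mm³ | % of baseline | CI half-width, mm³ | CI wholly below 0 |
|---|---|---|---|---|---|
| 0.6 | 0.95 | −27 | 0.4 | 308 | 3.7% |
| 0.6 | 0.9 | −55 | 0.8 | 432 | 4.6% |
| 0.6 | 0.8 | −115 | 1.7 | 606 | 5.6% |
| 0.6 | 0.7 | −179 | 2.7 | 729 | 7.3% |
| 0.8 | 0.95 | −43 | 0.6 | 488 | 3.8% |
| 0.8 | 0.9 | −89 | 1.1 | 685 | 4.6% |
| 0.8 | 0.8 | −186 | 2.4 | 953 | 6.4% |
| 0.8 | 0.7 | −293 | 3.8 | 1143 | 8.2% |

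The shift is 9 to 26% of the half-width. Without the cut it is within 2 mm³ of zero, and the CI falls below zero in 2.3 to 2.4% of trials.

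**Sensitivity to the median (ρ 0.9 to 0.7).** At 6000 (84 to 89% above the cut) the last column is 3.4 to 5.4%. At 4000 (66 to 70% above) it is 6.5 to 15.3%. The largest shift on the whole grid is at median 4000, CV 0.8, ρ = 0.7: 6742 to 6348 mm³, which is −394 mm³ or 5.8% of baseline.

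**Normal volumes, common-SD change.** The shift is −(1 − ρ)·SD·φ(z)/f with z = Φ⁻¹(1 − f). At f = 0.90 and ρ 0.9 to 0.7, the CI lies below zero in about 5.5 to 9% of null trials. At f = 0.70, where all 30 losses are due to the cut, it is 15 to 38%; that is an extreme case.

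**Change divided by own baseline.** At median 5000 and ρ 0.9 to 0.7, the null shift is +1.3% to +5.5% with the cut and +3.2% to +16.0% without it. The cut still lowers the mean, but the net is positive and the CI lies below zero in only 0.7 to 1.3% of trials. Other lognormal settings (CV 0.5 or 0.7, 70 to 90% above the cut, ρ 0.95 to 0.7) give −0.9% to +8.0%, so the sign is not fixed on this scale.

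**The case against.** **The primary endpoint may be untouched.** This stands in part. The bias is shown for the secondary mm³ endpoint and for one reading of the primary. On an own-baseline reading the main case is conservative. A reader might infer that the primary result is biased toward benefit however it is computed; the protocol does not support that, because it leaves the scale open.

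**The effect is small and every input is assumed.** This also stands. In the main case the shift is at most about a quarter of the CI half-width. A reader might go further and conclude that the Week 6 result cannot be interpreted at all. That does not follow: on the lognormal grid selection accounts for at most about 6% of baseline, and a reduction well beyond that could not be put down to it.

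**Week 24 offers a check.** It does in part. Section 5.2.1 gives a delivery period of about three months, and regression from the selecting scan would persist at Week 24, so a rebound by then would argue against it. A lasting drug effect would look the same as persisting regression, however, so this is not a clean separation.

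**These are matters for the SAP.** The definition of standardized is, and its absence here is not the point. The shift arises from elements that the protocol itself fixes: the cut, the single scan, the endpoint and the single arm. The optional sensitivity analyses in 9.2 concern missing data and baseline imbalance. The SAP was not available and may already add an analysis without the cut.

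**No null value is stated.** True. Comparing the CI with zero is an inference from the 95% CI and the 0.05 level in 9.2; the shift in the estimate does not depend on it.

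**Conclusion.** The concern holds in a limited form. Selecting on the baseline reading with no control makes the expected null change negative for absolute change in mm³, and for standardized change if the divisor is a common SD. No net direction is claimed for change relative to own baseline. The direction rests only on exchangeable readings under no effect and on some readings being able to cross the cut.

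The size cannot be fixed from the protocol. Under the stated assumptions with median 5000 mm³ and correlation 0.9 to 0.7, it is about −55 to −295 mm³ (0.8 to 3.8% of baseline), with a false signal of reduction in about 4.5 to 8% of null trials instead of 2.5%. It is smaller if most volumes lie well above 3000 mm³ or repeatability is high, and larger if many lie near the cut. A small observed reduction could therefore be partly selection. That the selected set is the primary one is read from 6.1, 9.1.1 and 9.3. Selecting patients with synovitis is a legitimate target; the weakness is only that no estimate free of the selection stands beside it.

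**What to change.** Keep the Synovitis Imaging Population as primary. Before the Week 6 interim analysis, add to 9.4.3: *Week 6 absolute and standardized change in synovial volume, with 95% CI, will also be reported for all Imaging Population patients with a quality Week 6 MRI, without the 3000 mm³ cut, beside the primary result.* The Week 6 condition is needed because the Imaging Population also admits patients whose only later scan is at Week 24. The mm³ row is the one free of the selection shift; an own-baseline row would not be centred on zero under no effect even without the cut.

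A regression-to-the-mean correction over a stated correlation range, for example 0.7 to 0.95, could be shown as an optional sensitivity analysis for mm³ or common-SD change only. Its correlation would be assumed, since no untreated repeat scan exists to check it.

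The cost is one table from data already collected. The drawback is dilution: patients with little synovitis have less to lose, so a smaller change without the cut does not by itself prove selection bias. Other single-arm biases remain, such as entry on a minimum pain score and, where pain is equal, choice of the more inflamed knee (7.4.2).

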9.2.2. Study Data

Study data identified in this protocol are collected, and source verified, on electronic Case Record Forms (eCRF) at sites completing the study. All study data will be formulated into data sets to provide transparency, traceability, and integrity of trial analysis results from collection source.

9.2.3. Study Variables for Assessment

Please refer to Section 7.7 for study variables.

9.2.4. Sub-Groups and Covariates

Sub-groups may be defined and explored and will be documented in the Statistical Analysis Plan.

9.3. Determination of Sample Size

Approximately 100 patients will be enrolled to ensure a minimum of 70 evaluable Synovitis Imaging patients, as defined by pre-treatment MRI synovial volume measurement of greater than 3000 mm³ of gadolinium enhancement as determined by quantitative image analysis, with quality Pretreatment and Week 6 MRIs. Previous trials had similar sample sizes ([Gait et al., 2016](#)) ([O'Neill et al., 2016](#)).

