7.4. Selection of Study Population

7.4.1. Number of Patients

Approximately 100 patients will be enrolled and treated with a single IA injection of 32 mg FX006 to ensure a minimum of 70 evaluable Synovitis Imaging patients, as defined by pre-treatment MRI synovial volume measurement.

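### Does the protocol's promise of at least 70 evaluable patients from about 100 enrolled need repair, given that nothing selects on synovial volume?

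*Protocol*

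**What the plan says.** Section 9.3 sets the sample size in one sentence: "Approximately 100 patients will be enrolled to ensure a minimum of 70 evaluable Synovitis Imaging patients". It describes those patients as having a pre-treatment volume "greater than 3000 mm³ of gadolinium enhancement as determined by quantitative image analysis, with quality Pretreatment and Week 6 MRIs". The only support offered is that earlier trials were of similar size. No effect size, standard deviation, power, evaluable share or loss rate is stated.

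The count is described in three places, with different detail:

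- **Section 7.4.1** (and the synopsis entry on number of patients): "to ensure a minimum of 70 evaluable Synovitis Imaging patients, as defined by pre-treatment MRI synovial volume measurement". It gives neither the threshold nor a Week 6 requirement.
- **Section 9.3** (and the synopsis entry on sample size): volume above 3000 mm³ plus quality pre-treatment and Week 6 scans.
- **Section 9.2.1** (and the synopsis entry on statistical methods), which defines the Synovitis Imaging Population: the Section 9.3 conditions plus a further one, "In addition, the patients included in this population will have no major protocol deviations and/or imaging variations".

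On selection, Section 7.9.6 says: "Once eligibility is confirmed, a pre-treatment MRI will be obtained and submitted to the central imaging facility to confirm image quality". The eligibility lists in Sections 7.4.2 and 7.4.3 contain no condition on synovial volume. Ultrasound enters only as a tie-break for choosing the index knee. The 2 mm thickness definition in Section 7.9.5.2 is tied to no entry rule.

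**The concern.** Seventy is the only planning number for the primary endpoint, and the protocol presents it as secured. Yet membership of the primary analysis set depends on a baseline volume that is not an entry condition. The number of patients above 3000 mm³ is therefore left to case mix. There is no instruction to keep enrolling until 70 qualify. Replacement under Section 7.5.10 is discretionary and covers only patients who discontinue.

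If 70 out of 100 is read as an expected yield of 70%, reaching the minimum is close to an even chance. The varying descriptions add a second worry: a running count kept on volume alone, or without the deviation and imaging-variation exclusion, would overstate the size of the set that is analysed. The primary estimate could then come from fewer patients than readers were led to expect, without any rule being broken.

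**Working it through.** **Inputs from the protocol.** Enrolment N = 100 (approximate) and evaluable minimum 70 (Section 9.3). The evaluable share p is not given, so every p below is an assumption.

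**Can 100 and 70 be reproduced?** Only by back-solving. 70 / (1 − d) = 100 gives d = 0.30. The protocol states no loss of 30%, so there is no stated calculation to find in error.

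**Chance of reaching 70.** With X distributed Binomial(100, p):

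| Assumed p | P(X ≥ 70) |
|---|---|
| 0.60 | 0.025 |
| 0.65 | 0.173 |
| 0.70 | 0.549 |
| 0.75 | 0.896 |
| 0.80 | 0.994 |

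Solving for p at N = 100 gives 0.751 for a 90% chance and 0.766 for 95%. If 10% are lost for reasons other than volume, 95% assurance needs 0.766 / 0.90 = 0.851 of enrolled patients above 3000 mm³. If 15% are lost, it needs 0.766 / 0.85 = 0.901. The answer therefore runs from very unlikely to near certain over a plausible range of p, and the document does not locate p within it.

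**Effect of the differing definitions.** Assume 80% exceed the threshold and 90% have both quality scans.

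- Section 9.3 wording: p = 0.80 × 0.90 = 0.72; expected 72; P(X ≥ 70) = 0.715.
- Section 9.2.1 wording, with a further 5% lost: p = 0.72 × 0.95 = 0.684; expected 68.4; P(X ≥ 70) = 0.411.

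The expected difference is 72 − 68.4 = 3.6 patients. The probability moves a good deal because 70 lies near the centre of the distribution, but the sample size hardly moves. With enrolment at about 100, the analysed set is the Section 9.2.1 set whichever wording is used for the count.

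**If enrolment were stopped on a volume-only count of 70.** Two later losses of 5% each leave 70 × 0.95 × 0.95 = 63.2. Two of 10% each leave 70 × 0.90 × 0.90 = 56.7. This describes a rule the protocol does not contain: enrolment is set at about 100, not at a running count of evaluable patients.

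**What a shortfall would cost.** The primary result is a mean change with a 95% confidence interval. Its half-width in standard deviation units is t(0.975, n − 1) / √n:

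| n | Half-width (SD) | Relative to n = 70 |
|---|---|---|
| 70 | 0.238 | 1 |
| 63 | 0.252 | 0.252 / 0.238 = 1.06 |
| 60 | 0.258 | 0.258 / 0.238 = 1.08 |
| 57 | 0.265 | 0.265 / 0.238 = 1.11 |

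Even the lowest of these counts widens the interval by about 11%.

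**The case for a change.** The strongest case for a change is that the protocol itself fixes these words and they do not agree, so this is not merely detail left to the analysis plan. Section 9.3 names Synovitis Imaging patients but leaves out an exclusion that defines that population, and ensure has no mechanism behind it. Losses between the two wordings are plausible, since follow-up scans must use the same machine, coil and software and NSAIDs are barred through Week 6. The repair would be wording only.

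The textual observations stand. Three things weaken the inference drawn from them.

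- A minimum of 70 is a floor. Setting a floor of 70 from 100 does not imply an expected yield of 70%; it suggests the sponsor expected more. The near-even chance belongs to a reading the protocol does not make.
- The loss assumptions ignore provisions that reduce losses. Section 7.9.6 requires a quality scan before dosing, calls for a repeat scan after a quality failure both before treatment and within the follow-up window, and requires the same equipment throughout. Section 7.5.10 allows replacement of patients who discontinue. None of these guarantees 70, but each bears on the assumed losses of 10% or 15%.
- The descriptions are nested rather than contradictory. Section 7.4.1 gives no threshold, so it can only be shorthand for a population defined elsewhere.

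**Conclusion.** No change to the plan is called for. The assurance is unsupported, because the protocol gives no evaluable share, but it is not shown to be false: 100 patients give a 95% chance of at least 70 if the joint share is about 77% or more. The binomial figures assume independent patients with a common share, and the share itself is an assumption throughout.

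The one real discrepancy is a clause missing from Section 9.3 and the matching synopsis entry. Section 9.2.1 defines the analysis set without ambiguity, so an analyst would build the same primary set either way. Falling short costs only precision, at most about 11% in interval width for the counts considered here, and no power statement or success criterion depends on reaching 70. Softening one verb and repeating a definition would be an editorial improvement that alters no procedure, analysis or conclusion.
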